- 2) Determine whether approximately 2-18 doses of optimal statin supplementation is sufficient by comparing whether patients randomized to receiving statin supplementation each individually experience a higher incidence of eCD and dCD than those patients on a pre-existing maximal dose of the three most common statins, and whether statins that pass the blood-brain barrier better correlate with reduced eCD and dCD.
 - 3) Determine whether patients on no pre-existing statin regimen exhibit less eCD and dCD when randomized to 2-18 doses of pre-operative maximal dose atorvastatin (80mg) compared to minimum dose atorvastatin 10mg.
 - 4) Determine a dose-response relationship to these 3 statins by determining whether all patients at the time of surgery have less eCD and dCD if they are on: 1) simvastatin 40mg rather than on <40mg; 2) atorvastatin 80mg rather than on <80mg; and 3) rosuvastatin 20mg rather than on <20mg.

The secondary study objectives are to:

- 1) Determine whether a pre-operative statin regimen alters the prevalence of early mortality at Day 365 +/- 30.
- 2) Determine whether differences in eCD/dCD identified in Primary Objectives 1- 4 are associated with either:
 - a. levels of, or peri-operative changes in, ESR/CRP, and/or
 - b. changes in either activities of daily living (BLESSED) or cognition (TICS-M) in the year following randomization and surgery.

Design and Outcomes

This is a phase III study for patients with carotid artery stenosis designed to assess if maximizing statin doses for (2-18) prior to carotid endarterectomy (CEA) is neuroprotective. All patients undergoing this procedure and who can tolerate the statin regimen will be asked to participate in this multi-center study. If patients are already on a statin, then only patients on *atorvastatin*, *simvastatin*, or *rosuvastatin* will be recruited. Subject participants will be grouped to one of three arms as a function of their pre-existing statin regimen, or lack thereof. Throughout the term of the study, subject participants will be closely monitored for medication compliance as well tolerance and safety via phone calls and in person.

The randomization will be stratified by center, previous use of statin and in random blocks of 4 and 6.

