2.2 Study Rationale

CEA reduces the risk of future stroke in this patient population by 55-65%, but its effectiveness is dependent on very low peri-operative morbidity, especially in patients presenting with asymptomatic disease. Recent improvements in the medical management of patients with asymptomatic stenosis have improved the outcome for un-operated patients to such a degree that some have even questioned whether the benefits of asymptomatic CEA still justify its risks. The rate of peri-operative stroke has fallen precipitously over the same period to less than 1.5%. It is critical that peri-operative management continue to evolve if the neuroprotective effects of CEA are to be realized for all CEA patients. Given that post-CEA stroke is so rare, investigators have increasingly looked to subtler, although more common, forms of cerebral injury to inform treatment decisions and improve procedural safety. eCD affects ~25% of patients undergoing CEA and ~15% of undergoing asymptomatic CEA. It is associated with marked elevations in tissue markers of cerebral injury (S100B) and is associated with earlier post-CEA mortality (1-3).

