4.1 Inclusion Criteria

- 1) Age ≥ 18 years of age.
- 2) Patient is currently on atorvastatin or simvastatin or rosuvastatin or statin naïve (no statins in the last 30 days).
- 3) The patient has unilateral or bilateral carotid artery stenosis that is considered severe (carotid artery diameter reduction $\geq 70\%$) as defined by any of these: a) Peak systolic velocity of at least 230 cm/s OR
b) CTA showing $\geq 70\%$ stenosis OR
c) MRA showing $\geq 70\%$ stenosis
- 4) The patient's attending doctor(s) (PMD, cardiologist, vascular/neurosurgeon) AND the patient have decided to proceed with a CEA to treat the patient's severe carotid stenosis.
- 5) The patient has no known circumstance or condition likely to preclude 1 year follow-up or adherence to the study protocol.
- 6) The patient is independent in their Activities of Daily Living at baseline (without cognitive, hearing or visual impairments which would impede NP testing). Walking impairments will not be a reason for exclusion.
- 7) Patient has the ability to provide informed consent.

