9.2 Sample Size and Randomization

Power Analysis

All of the aims will use logistic regression with presence of eCD as the response variable as the primary statistical analysis. A separate independent analysis for dCD will also be performed. Power calculations used data simulations (1000 simulations for each) with power=0.8, $\alpha=0.05$, and expected rates of eCD

based on existing preliminary data. For the comparison between subjects in arm 1 with a maximal dose (N=225) and those in arm 2 beginning with a sub-maximal dose and increasing to a maximal dose (N=338), the estimated minimum detectable effect size corresponds to a 65% reduction in eCD in the former cohort vs. the latter. For the comparison in between subjects in arm 2 beginning with a sub-maximal dose and increasing to a maximal dose (N=338) and those staying at the sub-maximal dose (N=337), the estimated minimum detectable effect size corresponds to a 46.7% reduction in eCD in the former cohort vs. the latter. For the comparison between subjects in arm 3 with 80 mg of atorvastatin (N=50) and those with 10 mg of atorvastatin (N=338), the estimated minimum detectable effect size corresponds to a 91.3% reduction in eCD in the former cohort vs. the latter.

Rationale for Sample Sizes

As per the power analysis above, the 1000 targeted patient enrollment is reasonable considering the aims of this study. We anticipate approximately 350 patients will be scheduled for CEA per year from the six participating institutions (Columbia-Presbyterian, St. Luke's Roosevelt, Cornell University, Valley Hospital, Montefiore Medical Center, and Buffalo Medical Center). Approximately 80% are anticipated to be asymptomatic, leaving 280 per year.

Expecting an approximate 75% recruitment rate, 210 eligible asymptomatic patients will be enrolled each year from the six sites. Over five years, this rate allows for 1000±50 patients to be enrolled. Based on our previous R01 grant, we estimate that a) 225 patients will already be on a pre-existing maximal statin regimen of simvastatin, atorvastatin, or rosuvastatin, b) 675 patients will be on a sub-maximal statin regimen of simvastatin, atorvastatin, or rosuvastatin, and c) 100 patients will be on no pre-existing statin regimen.

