This is a phase III study for asymptomatic patients with carotid artery stenosis designed to assess if maximizing statin doses for approximately two weeks (12-18 days) prior to carotid endarterectomy (CEA) is neuroprotective. Patients who are already on the maximal statin dose of either atorvastatin (80 mg), simvastatin (40 mg) or rosuvastatin (20 mg) will remain on their current doses and will be part of our observational arm. The patients that are currently on sub-maximal daily doses of the previously mentioned statins will be randomized to either 1) their current dose plus placebo or 2) their current dose plus the necessary milligrams needed to bring them to the FDA approved maximal dose per day for their corresponding statin. Those patients who are statin naïve, 30 days prior to enrollment, will be randomized to daily doses of either 1) 10 mg of atorvastatin or 2) 80 mg of atorvastatin.

We will stay in contact with Mr./Mrs. _____ via phone calls prior to the CEA to assure study drug compliance and safety. We will also assess him/her prior to the CEA, 12-25 hours post-CEA, and during their post-operative clinical visit (approximately at 30 days post-CEA) for early cognitive dysfunction (eCD). The final follow-up phone call will be one year after their CEA procedure.

We have attached a copy of your patient's study consent form. We ask that you not alter your patient's assigned statin dose unless it is clinically necessary. If you do change their dose prior to their CEA, please let us know. After their CEA, Mr./Mrs. _____ will be prescribed statins as per the standard of care for post-CEA patients by their treating physician and will not receive any further study drugs.

If you have questions, please do not hesitate to contact our Study Clinical Coordinator, [name of coordinator] at [contact number] or one of us.

Sincerely yours,

[Contact Information for Principal Investigator at Site]

• Appendix VI: Delegation of Authority Log

STANCE TRIAL
SITE PERSONNEL SIGNATURES & DELEGATED RESPONSIBILITIES LOG

Study Site: _____

NAME (PRINT OR TYPE)	SIGNATURE	INITIALS	STUDY ROLE (i.e. Site PI, Study physician, sub-investigators, Study Coordinator, Research Pharmacy, etc)	DELEGATED RESPONSIBILITIES* (list all that apply A-I)	DATES (Involved in STUDY) (mm/dd/yyyy)	PI Initials/Date (mm/dd/yyyy)
					Start: _____ Stop: _____	
					Start: _____ Stop: _____	
					Start: _____ Stop: _____	
					Start: _____ Stop: _____	
					Start: _____ Stop: _____	

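### Symptomatic CEA patients are eligible, but the accrual count and the doctor letter cover asymptomatic patients only, and no control rate or source population is stated for the 46.7% detectable reduction

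*Combined protocol and SAP*

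**What the plan says.** **Eligibility.** The Precis (Design and Outcomes) states: "All patients undergoing this procedure and who can tolerate the statin regimen will be asked to participate in this multi-center study". Section 4.1 asks for severe stenosis ("The patient has unilateral or bilateral carotid artery stenosis that is considered severe") and that the doctors and the patient "have decided to proceed with a CEA to treat the patient's severe carotid stenosis". Nothing in Section 4.1 or 4.2 mentions symptoms, previous stroke or TIA.

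**Accrual.** Section 9.2 starts from all CEA patients: "We anticipate approximately 350 patients will be scheduled for CEA per year from the six participating institutions". It then restricts them: "Approximately 80% are anticipated to be asymptomatic, leaving 280 per year". After a 75% recruitment rate it arrives at "210 eligible asymptomatic patients will be enrolled each year from the six sites", and so at 1000±50 over five years.

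**Doctor letter.** Appendix V opens: "This is a phase III study for asymptomatic patients with carotid artery stenosis". The matching sentence in the Precis does not contain the word asymptomatic.

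**Power.** Section 9.2 gives power 0.8, alpha 0.05 and a 46.7% minimum detectable reduction for Arm 2 (338 v 337). It refers to rates from preliminary data without giving a number, a population or the sidedness.

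**Preliminary rates.** Section 2.2 states: "eCD affects ~25% of patients undergoing CEA and ~15% of undergoing asymptomatic CEA".

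**Analysis.** Randomisation is stratified by centre and previous statin use (Section 9.2.1). Symptomatic status is not named in the variable lists of Sections 9.1 and 9.5. Covariate adjustment is reserved for risk factors out of balance at p<0.10.

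**The concern.** The plan describes two populations. Under the eligibility criteria a patient with a recent TIA can be randomised. Under Section 9.2 that patient was removed before anyone was counted. The doctor of such a patient would receive a letter saying that the study is for asymptomatic patients.

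Three things are at stake. The accrual forecast does not describe the patients who may be enrolled. The detectable effect cannot be checked, because it depends on a control rate that is not given, and Section 2.2 quotes clearly different rates for all CEA and for asymptomatic CEA. And a baseline characteristic that the sponsor used to classify its own earlier cohort has no stated place in the stratification or the primary model.

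**Working it through.** **1. Accrual (Section 9.2 inputs: 350 a year, 80% asymptomatic, 75% recruited, five years).**

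- As planned: 350 × 0.80 = 280; 280 × 0.75 = 210 a year; 210 × 5 = 1050. This reproduces 1000±50.
- Without the asymptomatic step: 350 × 0.75 = 262.5 a year; × 5 = 1312.
- Time to reach 1000: 1000/210 = 4.8 years against 1000/262.5 = 3.8 years.

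Both totals use the volume of six institutions. The list of participating sites has ten, and three of the six (St. Luke's Roosevelt, Cornell and Montefiore) are not on it. Neither total therefore describes the current trial.

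**2. Control rate behind 46.7%.** It cannot be reproduced directly, so I solved for the control rate p1 at which p2 = 0.533 × p1 gives 80% power with 337 v 338 and two-sided alpha 0.05 (assumed, since sidedness is not stated):

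power = Φ{[(p1 − p2) − 1.96·√(p̄(1−p̄)(1/n1 + 1/n2))] / √(p1(1−p1)/n1 + p2(1−p2)/n2)}

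At p1 = 0.145: p2 = 0.0773, p̄ = 0.111, null SE 0.0242, alternative SE 0.0241. Then (0.0677 − 0.0474)/0.0241 = 0.84 and Φ(0.84) = 0.80. The control rate is about 14.5%; a simulated logistic Wald test gives about 14.4%.

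- One-sided, the answer is 11.7%. If 46.7% is read as a reduction in odds, it is 18.0%.
- The pooled asymptomatic preliminary rate in Section 2.1.5 is (200 × 11.0% + 124 × 20.2%)/324 = 14.5%.
- The asymptomatic rate in Section 2.2 is about 15%, and 15% v 8% is a 46.7% reduction (power 0.81).
- None of the three readings gives the 25% that Section 2.2 quotes for all CEA.

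**3. Sensitivity of the Arm 2 detectable effect (same formula, two-sided).**

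| Control rate | Basis | Detectable reduction at 80% power | Power for 46.7% |
|---|---|---|---|
| 11% | asymptomatic statin users, Section 2.1.5 | 53.3% | 0.67 |
| 12% | 2007-2012 series, Section 2.1.5 | 51.2% | 0.71 |
| 14.5% | back-solved | 46.7% | 0.80 |
| 15% | asymptomatic CEA, Section 2.2 | 45.9% | 0.82 |
| 17% | mix: 80% at 15%, 20% at an assumed 25% | 43.1% | 0.87 |
| 20% | mix: 80% at 15%, 20% at an assumed 40% | 39.5% | 0.92 |

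**4. Bounding scenario: no effect at all in symptomatic patients.** Assume 20% symptomatic with an eCD rate of 25% to 39%, and a 46.7% reduction in asymptomatic patients only.

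- At 25%: control 0.8 × 0.15 + 0.2 × 0.25 = 17.0%; treated 0.8 × 0.15 × 0.533 + 0.05 = 11.4%; pooled reduction 33%; power 55%.
- At 39%: control 19.8%; treated 14.2%; pooled reduction 28%; power 49%.

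The 39% comes from taking 25% as the overall rate in the earlier cohort of 231 symptomatic and 328 asymptomatic patients: (0.25 − 0.587 × 0.15)/0.413 = 39.2%. No symptomatic rate is stated in the documents.

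**The case against.** The best defence is that only wording is at fault. The asymptomatic patients are the expected 80% of the eligible population, not a different one. Admitting the other 20% raises accrual and, if they have more events and the same relative benefit, improves the detectable effect. Randomisation protects validity whether or not symptomatic status is in the model. Medical history is collected at baseline, imbalance-driven adjustment is planned, and Section 9.1 allows post-hoc subgroup assessments. Much of this stands, and it rules out several stronger readings that a reader might infer.

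- **That the trial is too small.** The rate in a mixed population is not documented, and step 3 runs in both directions. Every Arm 2 patient is already on a statin, so 11% or 12% is as arguable as 17% to 20%.
- **That symptomatic patients have about 39% eCD.** Section 2.1 gives the 25% as an upper figure for statin-naive patients, and Section 2.1.5 reports incidence falling from 24.2% to 12.0%. The 25% is not a secure overall rate for a statin-treated trial.
- **That statins work less well in symptomatic patients (P=0.19 against P=0.04).** A larger P value in a smaller group does not show a weaker effect. Section 2.1.5 calls the decrease similar, and Section 2.1.7 says that the effect is also present in symptomatic stenosis. The 55% to 49% power is therefore a bound, not a forecast.
- **That symptomatic status is one of the strongest risk markers.** Sections 2.1.2 and 2.2.1 name age, diabetes and genotype, not symptomatic status.

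The defence does not remove the conflict between the eligibility criteria, Section 9.2 and Appendix V, or supply the missing control rate. A rule that adjusts only when imbalance reaches p<0.10 is also not prespecified adjustment for a named covariate.

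**Conclusion.** The contradiction is documented and needs no inference: eligibility takes all CEA patients, while the accrual count and the doctor letter take asymptomatic patients only. In accrual it amounts to 1050 against 1312 over five years, on a six-site volume that is itself out of date.

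That the 46.7% rests on an asymptomatic control rate is plausible. The two-sided back-calculation of 14.5% matches the pooled asymptomatic data, but it assumes a two-sided test and a relative reduction in risk, and the documents state neither. Over control rates of 11% to 20% the detectable reduction runs from about 53% to 40%. This shows that the stated figure cannot be assessed for the enrolled population; it does not show that 1000 patients is inadequate. The point should be corrected, but it does not undermine the randomised comparison.

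**What to change.** 1. Decide whether symptomatic patients are enrolled. Make Sections 4.1 and 9.2 and Appendix V agree, and recompute accrual for that population and the current sites.
2. State the control eCD rate, its source population and the sidedness behind 46.7%, and restate the detectable effect for the population enrolled.
3. If both groups are enrolled, record symptomatic status from the medical history already collected and give the expected mix. Include it as a prespecified covariate in the primary logistic model, whatever the baseline imbalance, and report the treatment effect by symptomatic status as a prespecified supportive analysis. This is best settled before the Arm 2 interim analysis.

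The cost is revised wording in Section 9 and the letter, one derived baseline variable and a little more analysis. No extra patients are needed.

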9.2.1 Treatment Assignment Procedures

The randomization design will be stratified by center, previous use of statin and in random blocks of 4 and 6. The randomization process will be supported by the Statistical Analysis Center (SAC) at the Mailman School of Public Health at Columbia University. SAC will provide a central secure web-based randomization data system. All trials supported by the SAC employ central randomization that takes place in real-time. In other words, the patient's treatment assignment is made at the moment of randomization, based on probabilities calculated according to the randomization scheme, and communicated to the recruiting site via a central source (i.e. a secure web site).

- Patients on maximum dose of one of the three statins will be maintained on that dose (ARM 1). This arm will contain 225 participants.

- Those patients on submaximal doses of the 3 study statins will be randomized to their current dose plus placebo or their current dose plus the additional milligrams necessary to bring to raise them to the maximal daily dose of simvastatin (40 mg) or atorvastatin (80 mg) or rosuvastatin (20 mg) depending on which statin they are already on, (ARM 2). There will be 337 participants maintained at their current dose and 338 raised to the maximum dose of their statins.
- If patients are statin naïve, then they will be randomized to either atorvastatin 10 mg or 80 mg daily (ARM 3). ARM 3 will have 50 participants in each arm.

The randomization will be performed automatically by the web-based data system. No one will have access to unblinded treatment information on a regular basis other than the packaging pharmacy. All handling of study medication will take place using blinded bottle codes. It is not expected that serious adverse events will require revelation of treatment assignment, but the study web site will provide for online unblinding in emergencies. Revelation of treatment assignment will be available only to authorized users, who will be required to provide a clinical justification for unblinding. Each case of unblinding will be addressed by study personnel to ensure access to unblinded treatment assignment information is limited, and that such incidents are limited to circumstances where it is necessary for the health of the patient.

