20.2%, $P=0.03$) than those not taking statins (2). Within the asymptomatic population, patients taking simvastatin exhibited significantly less eCD than those taking atorvastatin (3.0% vs. 16.0%, $P=0.005$) (Figure 5). There were no other significant pairwise differences in eCD among the other statin types (13). There were significant pairwise differences in HDL among statin types. HDL levels were higher in patients taking simvastatin compared to those taking atorvastatin ($P<0.001$). There were significant pairwise differences in LDL levels only between simvastatin and atorvastatin ($P=0.003$). However, there were no significant differences in triglycerides or total cholesterol levels among the statin types (13). Patients taking statins had significantly lower pre-operative monocyte counts than those not taking statins (7.0 ± 2.0 vs. $8.2\pm 2.1 \times 10^9/L$, $P<0.001$) at the time of surgery. However, there were no differences in monocyte counts amongst the statin types. The central question that we hope to answer is whether statin neuroprotection depends on the type of statin (simvastatin, atorvastatin or rosuvastatin and/or lipophilic versus non-lipophilic) or dose of statin.

A similar decrease in eCD was also seen in symptomatic and asymptomatic patients not taking and taking statins, and if looked at when both groups are analyzed together (symptomatic and asymptomatic patients together): $P=0.04$ (Asymptomatic), $P=0.19$ (Symptomatic), and $P=0.015$ (together).

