2.2.1 Hypothesis

While there are several non-modifiable risk factors for eCD after CEA identified from previous research, including medically treated diabetes mellitus and the presence of the ApoE-ε4 genotype, we have only been able to identify one potentially neuroprotective factor, namely preoperative statin use. Consequently, we hypothesize that in CEA patients:

- 1) A pre-operative statin regimen is protective against eCD (12-25h) and dCD (30d); consequently, early (365d) mortality.
- 2) Maximal doses may be essential in achieving optimal neuroprotection against eCD and dCD, with lipophilic statins or those that pass the blood-brain barrier more easily achieve similar effects at lower doses.

3 **STUDY DESIGN**

[figure not shown]
This is a Phase 3, multicenter, observational (ARM 1), randomized and double-blind study (ARM 2 and ARM 3), and placebo-controlled (ARM 2), where 1,000 carotid stenosis outpatient participants will be assigned to a specific daily statin regimen of no fewer than 2 and no greater than 18 doses prior to their CEA.

We will include patients who are either statin naïve, assuming no history of adverse experience with a statin, or on one of three types of statins: simvastatin, atorvastatin, or rosuvastatin. Patients will be enrolled, and based on their preexisting statin regimen, they will be grouped into one of three arms prior to CEA: ARM 1) Patients on a pre-existing maximal daily dose statin regimen will be observed, ARM 2) Patients on a pre-existing statin regimen at sub-maximal doses will be randomized to maintain their current dose plus placebo or current dose plus the necessary milligrams to reach maximal daily dose, and ARM 3) Patients who are on no preexisting statin regimen, statin naïve in the last 30 days, will be randomized to atorvastatin

10mg or atorvastatin 80mg for no fewer than 2 and no greater than 18 daily doses before their CEA (Figure 6).

As per the simvastatin drug insert, patients taking amlodipine (Norvasc) should not exceed 20 mg of simvastatin; therefore, we will only potentially increase any patient who is also on amlodipine to daily doses of 20 mg and not 40 mg. Consequently:

- *If subject is on 40 mg simvastatin without amlodipine – they will be in ARM 1 (observational)
- *If subject is on 40 mg simvastatin + amlodipine – they will be in ARM 1 (observational)

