Investigators will not be involved in preparation or delivery of drug to maintain the blind. BRINM has prepared blinded and randomized drug supplies for several randomized trials. It will provide all pharmacy support for the study, including preparation of the randomization schedule, placebo and active statin drug supplies, monitoring of procedures for shipping drug to multiple sites, and documentation of drug handling and disposal of remaining study drug at its site.

Inventory will be monitored by BRINM to make sure that we maintain at least 3 bottles for each randomization option for any potential enrollment of subjects in ARM 2 and ARM 3. This will allow adequate inventory at each site for any potential randomization. Consequently, we will strive to maintain 24 bottles of study drug at each site [ARM 2 requires 6 study bottles for the atorvastatin group (3 placebo + 3 active drug for maximization); 6 study bottles for the simvastatin group (3 placebo + 3 active drug for maximization), and 6 study bottles for the rosuvastatin group (3 placebo + 3 active drug for maximization) while ARM 3 will require 3 bottles of 10 mg atorvastatin and 3 bottles of 80 mg atorvastatin.] Upon randomization of each subject, the study database will automatically send an email to BRINM to inform them of the bottle number used and the study option that needs to be replenished.

The study drug will be requested from the site's research pharmacy with a doctor's order, copy of 1st and signature page of the consent form, copy of the randomization page from the study website, site approved cover fax form, and in accordance with regulatory and pharmacy procedures. Study treatment is to be dispensed only to subjects enrolled in this study. Study treatment must be dispensed only by a pharmacist or appropriately qualified staff. Once study treatment is dispensed to a subject, it cannot be used for another. Study treatment bottles are only for the dosing period prior to CEA. None of the remaining capsules from one subject can be used for another subject.

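### The Arm 2 primary logistic model fixes neither centre nor statin type, and the second stratification factor has no stated levels: a modest loss of efficiency, cheaply repaired

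*Combined protocol and SAP*

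**What the plan says.** Section 9.2.1 states: "The randomization design will be stratified by center, previous use of statin and in random blocks of 4 and 6". The Precis and Sections 3, 4.3 and 6.2.3 name the same two factors. None of them lists the levels of the second.

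Arm membership already depends on statin history. For Arm 2, Section 3 says: "Patients on a pre-existing statin regimen at sub-maximal doses will be randomized". Section 9.2.1 agrees: "Those patients on submaximal doses of the 3 study statins will be randomized to their current dose plus placebo", or to that dose raised to the maximum. Arm 3 takes only patients with no statin in the preceding 30 days and randomises them between two atorvastatin doses. Arm 1 is observational.

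On analysis, Sections 9.2 and 9.5 make logistic regression on eCD the primary method for every aim, without a covariate list. Sections 9.1 and 9.5 say that regression will adjust for risk factors out of balance at p<0.10. Neither centre nor statin type is named as a term, although Section 9.1 records medication names and doses.

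On prognosis, the preliminary results in Section 2.1.5 say that "patients taking simvastatin exhibited significantly less eCD than those taking atorvastatin", with rates of 3.0% and 16.0%. Under its interpretation heading, Section 9.1 expects simvastatin to protect more than the other two statins.

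**The concern.** A stratification factor is useful when it varies among the patients being randomised. On the yes/no reading, previous statin use has one level in Arm 2 and one in Arm 3, so it balances nothing inside either. The drug-related variable that the protocol itself expects to predict eCD, statin type, is then balanced in Arm 2 only by chance.

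The analysis does not fill that gap. Covariates enter only after an imbalance test, so the model depends on the data. Just before stating the rule, Section 9.1 describes its two groups as patients with and without eCD, so it is not clear that treatment balance is what will be tested. It is also unclear whether statin type counts as a risk factor for this purpose. Centre is used in the randomisation but appears nowhere in the model.

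At stake are some avoidable noise in the main randomised comparison and some discretion over the primary model. Arm 2 is the largest arm and the only one with a formal interim analysis (Section 9.3).

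**Working it through.** **Inputs from the documents.** Arm 2 has 338 raised and 337 maintained (9.2.1). The preliminary statin counts are atorvastatin 94, simvastatin 66 and rosuvastatin 12; eCD is 3.0% v 16.0% (2.1.5). The detectable effect is a 46.7% relative reduction at power 0.8 and alpha 0.05 (9.2).

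**Assumptions.** Two-sided testing. The simvastatin share of Arm 2 is 66/172 = 38% (three statins) or 66/160 = 41% (simvastatin and atorvastatin only), with 20-50% as the range. The 13-point gap (16.0 - 3.0) applies in Arm 2.

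1. *The plan's own figures.* The rates match 2/66 and 15/94. The likelihood-ratio test gives P = 0.0049, agreeing with the stated 0.005; Pearson gives 0.0090. The Arm 2 power figure cannot be strictly reproduced, because no control rate is stated. Power of 80% at a 46.7% reduction needs a control rate of 14.5%. At 15% power is 81.5%, at 12% it is 71.3% and at 11% it is 67.1%. At 14.5% the detectable difference is 14.5 × 0.467 = 6.8 points.

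2. *Chance imbalance in the simvastatin share.* SD = √[p(1-p)(1/338 + 1/337)].

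| Share p | SD (points) | 1.96 SD (points) | Shift in eCD difference (× 0.13) |
|---|---|---|---|
| 20% | 3.1 | 6.0 | 0.79 |
| 38% | 3.7 | 7.3 | 0.95 |
| 41% | 3.8 | 7.4 | 0.97 |
| 50% | 3.9 | 7.5 | 0.98 |

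The shift is proportional to the gap: half the gap gives half the shift. An imbalance of 5 points or more has probability 18-19% at a 38-41% share and 10% at a 20% share. At the interim (446 patients, 38% share) the 1.96-SD shift is about 1.2 points.

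3. *Reach of the p<0.10 rule, if applied to statin type between treatment groups.* It triggers beyond 1.645 × 3.74 = 6.2 points. The largest shift left unadjusted is 6.2 × 0.13 = 0.8 points.

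4. *Effect on the test, by simulation.* 4,000 runs per setting, 675 patients, ten equal centres without centre effects, blocks of 4 and 6, 41% simvastatin, eCD 3% v 16%.

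| Randomised by | Model | Type I error | Power at 46.7% | Power, rates × 1.45 |
|---|---|---|---|---|
| Centre | Unadjusted | 4.7% | 64.7% | 82.7% |
| Centre × type | Unadjusted | 4.7% | 65.8% | 82.8% |
| Centre | Type | 4.1% | 66.7% | 84.9% |
| Centre × type | Type | 4.9% | 66.6% | 84.5% |

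The Monte Carlo SE of the power figures in the fourth column is about 0.75 points. Power there is near 65% because this mix implies a control rate of (94 × 16% + 66 × 3%)/160 = 10.6%, not because of the stratification. Scaling the rates by 1.45 brings the control rate to 15.4%. Stratifying by type cuts the SD of the share difference from about 3.8 to about 0.7 points, but adds no measurable power once type is in the model.

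The value of adding centre cannot be computed: the documents give no eCD rates by centre.

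**The case against.** The strongest reply is that the factor is undefined rather than shown to be empty. It may have meant which statin was used. Section 4.3 bases randomisation on the pre-existing regimen, and Section 5.2 stocks active and placebo bottles separately for each statin. Neither passage says that allocation lists are kept by statin type, but they leave that reading open. This stands, so the text needs a definition. Even as yes/no, the factor properly keeps separate lists for Arms 2 and 3.

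A second reply is that the 3.0% v 16.0% contrast is observational, comes from asymptomatic patients and pools all doses, including maximal doses that Arm 2 excludes. That also stands. It does not show that the gap is smaller in Arm 2: Sections 2.1 and 2.2 say the difference held at all doses except atorvastatin 80 mg, which Arm 2 excludes.

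A third is that the p<0.10 rule already handles serious imbalance. In part it does (step 3), if it is applied to statin type. Fixed terms do the same without a data-dependent choice.

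A reader might also infer that the per-statin comparisons in Objectives 2 and 4 are compromised, above all for rosuvastatin. The documents do not support this. Objective 2 compares maximised patients with non-randomised Arm 1, and Objective 4 pools all patients by dose within a statin, so stratifying Arm 2 cannot balance those parts. Within one statin, the mix of types cannot confound. On the preliminary mix, rosuvastatin gives about 675 × 12/172 = 47 patients. A split of 18:29 or worse has about a 14% chance under simple randomisation, yet 18:29 keeps 4 × 18 × 29/47² = 94.5% of the efficiency of an even split. The limit there is the number of patients.

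**Conclusion.** The point holds as one about efficiency and clear prespecification. On the plain reading, centre is the only stratifier at work in Arm 2, and the primary model fixes neither centre nor a statin type that the protocol expects to be prognostic. A 1.96-SD imbalance shifts the eCD difference by about 0.8-1.0 points over simvastatin shares of 20-50%, against about 6.8 points detectable. Power changes by about 1-2 points, most of it recovered by adjusting for type.

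A reader might infer that the randomised comparison is biased or its error rate inflated. It is not: chance imbalance is already part of the standard error, and simulated type I error was 4.1-4.9% in every setting. Nor does the evidence require a change to the randomisation.

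The sizes rest on the assumed statin mix, the observational 13-point gap, two-sided testing and, for the detectable difference, a 14.5% control rate. The simulated power figures also assume ten equal centres.

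**What to change.** For the Arm 2 comparison, prespecify centre and statin type (simvastatin, atorvastatin, rosuvastatin) as fixed covariates in the primary logistic model, in place of the p<0.10 imbalance rule. State the levels of the previous-statin factor. If the system already randomises within statin type, say so.

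The cost is a few model terms on data already collected. With ten centres there would be 9 centre terms, 2 for statin type and 1 for treatment, 12 in all. At 14.5% v 7.7% the expected events are 0.145 × 337 + 0.077 × 338 = 75, about 6 per term, so a rule for pooling small centres should be written in advance.

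Stratifying Arm 2 by statin type is optional. It gives tighter balance, but about 47 rosuvastatin patients over ten centres is roughly 5 per centre, so many blocks of 4 and 6 would stay incomplete.
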